Participants will be randomly assigned to one of two groups, EFT or ERT, and complete an episodic thinking task. Participants will be randomized by stratifying for education level and sex. The episodic thinking task to generate episodic cues will be similar to the tasks used in our previous studies on EFT's effect (Daniel et al., 2013). Each group will list and describe events for different time periods. The episodic component of the thinking task will occur while the participants are asked to describe what they are imagining about each event (e.g., vacations, weddings, parties, and so forth). EFT participants will list positive future events they are looking forward to and list events that could happen at different general future time points (e.g., 1 month, 2-6 months, 7-12 months). In contrast, the ERT group will list positive recent events (events that have already happened) that they have enjoyed that have occurred at different general time points (e.g., a few hours ago, 1 day ago, 2-6 days ago, 7-12 days ago). All participants will rate the salience, valence, arousal, feasibility and vividness of each event and events with the highest ratings for vividness will be used in the generation of episodic cues. An "imagery" score may be calculated by averaging the frequency/vividness scores for each event. Reductions in rate of discounting occur at higher levels of episodic imagery (Peters & Buchel, 2010). Additionally, participants will record their highest rated events into audio cues.

Participants may also be instructed to use and think about their episodic cues as they engage in a set of executive function tasks (e.g., The Virtual Week) and other decision making tasks such as measures of delay discounting (e.g., discounting of money, food, sedentary behaviors/physical activity, future health; a series of single and cross commodity discounting tasks) and food preferences. Participants will be randomized to which cues (future or recent) they will be instructed to think about when engaging in The Virtual Week task. Executive function tasks may take place on a computer screen or paper and pencil. Participants will complete questionnaires regarding their attention to their episodic cues while engaged in study tasks.

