fMRI Arm: If it is determined that the participant is willing and eligible to complete an fMRI they may be entered into the fMRI arm of this study. For these participants, the first visit is identical to that of the first visit in the behavioral arm of the study, with the exception that participants will not complete an episodic thinking task, and the MRI screening form may be reviewed with the participant to ensure safety and eligibility.

Eligible participants will be scheduled for an additional session to be completed within the next 30 days. The second session will last approximately an hour and a half to two hours. Participants may be asked to abstain from eating or drinking (except water) for approximately 2 hours prior to their sessions and engaging in any activity that may influence appetite. Participants who are not about 2 hours post prandial or have experienced a major life event that may influence their performance on study measures and tasks may have their appointment rescheduled. As in the first visit, participants will have their blood glucose measured and then offered a PowerBar to consume prior to completing all study related tasks. In this visit, participants will again have blood glucose measured three separate times (e.g. beginning of session, 30 minutes after consuming PowerBar, and at the end of the session).

In the second visit, female participant will again be asked to provide a urine sample to confirm non-pregnancy status. Eligible participants will be randomly assigned to one of two groups, EFT or ERT, and complete an episodic thinking task identical to the thinking task in the first visit of the behavioral study. They may also be asked to complete decision making tasks while engaged in episodic thinking and undergoing an fMRI without contrast scan at their second session. Prior to the scan, MRI safety trained personnel will assess the safety of all participants. During the fMRI scan, the participant will be given a small box with buttons to press in response to the display that appears on the screen above them within the machine. The participant will be selecting objects that they prefer in decision-making tasks. Additionally, interested participants may have the opportunity to receive a copy of their brain images.

Following their last session, all participants will be debriefed.

Pilot participants will complete identical procedures, but may complete fewer sessions and/or activities than those described above.

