Neuroimaging: The MRI data will be collected during approximate 60 min sessions that will include positioning participants in the scanner, collecting T1-weighted structural scans, and conducting target fMRI experiments. Some parameters may be modified to accommodate the specifics of this multisite study. MRI scanning performed at the Dent Neurologic Institute will be performed on a Philips Ingenia 3T system (200 T/m/s slew rate). T1 weighted anatomical images will be acquired with a 3D Turbo Field Echo (TFE) sequence at 1mm isotropic resolution and scanning parameters: Shot interval = 2500ms, TR = 7.7ms, TE = 3.5ms, FA = 8 deg., BW = 191.5 Hz/2.26 pixel, and SENSE parallel imaging factor of 2.2, for an acquisition time of 5 minutes and 10 seconds. MRI scanning at Virginia Tech Carilion Research Institute or at the Virginia Tech Corporate Research Center will be performed on a Siemens 3T Tim Trio system outfitted with a 45 mT/m gradient system (200 T/m/s slew rate). T1 weighted anatomical images will be acquired with a 3D MPRAGE sequence at 1 mm isotropic resolution and scanning parameters: TI = 900 ms, TR = 2.6 s, TE = 3 ms, FA = 8°, BW = 130 Hz/pixel, and GRAPPA parallel imaging factor of 2, for an acquisition time of 4 minutes and 38 seconds. fMRI data will be acquired using a T2* weighted single-shot EPI sequence, matched across the two sites (see also section 6.6.3). Whole-brain functional volumes will be acquired in 26 3.4-mm axial slices (with a 20% slice gap), each with 3.4 mm x 3.4 mm in-plane resolution. Additional fMRI imaging parameters include: TR = 2 s, TE = 25 ms, FA = 90 deg., BW = 1953 Hz/pixel.

10.4 Describe any source records that will be used to collect data about subjects (e.g. school records, electronic medical records).

Response:

Electronic medical records will be used. These will include records from patients at UBMD, Urban Family Practice, and additional records provided through the use of i2b2.

*10.5 Indicate whether or not **individual** subject results, such as results of investigational diagnostic tests, genetic tests, or incidental findings will be shared with subjects or others (e.g., the subject's primary care physician) and if so, describe how these will be shared.*

Response:

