12.0 Setting

12.1 Describe all facilities/sites where you will be conducting research procedures. Include a description of the security and privacy of the facilities (e.g. locked facility, limited access, privacy barriers). Facility, department, and type of room are relevant. Do not abbreviate facility names.

NOTE: Examples of acceptable response may be: "A classroom setting in the Department of Psychology equipped with a computer with relevant survey administration software," "The angiogram suite at Buffalo General Medical Center, a fully accredited tertiary care institution within New York State with badge access," or, "Community Center meeting hall."

Response:

This research will be conducted at the University at Buffalo (UB) and Virginia Polytechnic Institute and State University (VT) as well as their corresponding fMRI facilities. All facilities are locked and require key or badge access to enter in relevant research areas.

The UB team will conduct research at the Division of Behavioral Medicine Research Labs, located in G56, G58, G90 and 151 Farber Hall, University at Buffalo South Campus. The fMRI scans will be conducted at local fMRI facilities located at Dent Neurologic Institute ([name]).

The VT research team will conduct research at the Virginia Tech Carilion Research Institute, in Roanoke and Blacksburg locations. The fMRI scans will also be conducted at the Virginia Tech Carilion Research Institute, also in Roanoke or Blacksburg. Recruitment and screening will be in collaboration with Carilion Clinic Department of Family and Community Medicine in Roanoke and surrounding areas.

12.2 For research conducted outside of UB and its affiliates, describe:

- Site-specific regulations or customs affecting the research
- Local scientific and ethical review structure

NOTE: This question is referring to UB affiliated research taking place outside UB, i.e. research conducted in the community, school-based research, international research, etc. It is not referring to multi-site research. UB affiliated institutions include Kaleida Health, ECMC, and Roswell Park Cancer Institute.

Response:

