17.0 Data Management and Analysis

17.1 Describe the data analysis plan, including any statistical procedures. This section applies to both quantitative and qualitative analysis.

Response:

Analytic plan is to use factorial ANCOVA to compare between group differences in different measures of DD, executive function and fMRI-measured brain function for subjects randomly assigned to poverty/neutral conditions and EFT/ERT. Covariates will be used if significant differences between groups are observed in subject characteristics. We predict a main effect of neutral/poverty, such that those assigned to poverty will have higher DD than those assigned to neutral, and an interaction between poverty/neutral and EFT such that in the poverty condition, EFT will reduce the discounting to levels achieved by the wealth, ERT subjects. We also predict when participants who receive EFT under challenge of poverty that EFT will increase activation in brain regions associated with delay of gratification (LPFC and AC) and prospection (hippocampus) relative to those who receive EFT under similar challenges.

17.2 If applicable, provide a power analysis.

NOTE: This may not apply to certain types of studies, including chart/records reviews, survey studies, or observational studies. This question is asked to elicit whether the investigator has an adequate sample size to achieve the study objectives and justify a conclusion.

Response:

The sample size is based on our studies of EFT versus ERT on DD in overweight and obese subjects, which showed an average AUC of $0.54 + 0.28$, and our unpublished research that poverty simulations reduces DD by 34%. We estimate in the ERT condition, neutral simulations will lead to less discounting and higher AUC than poverty simulations (0.54 vs 0.36). We estimate in EFT conditions, that simulations of neutral are associated with a small improvement in discounting in comparison to poverty simulations (0.63 vs 0.54). These predictions suggest that DD in EFT/Poverty and ERT/Wealth will be equivalent. The effect size for this interaction is 0.35. Using the overall SD we observed of 0.28, alpha of .05 and power of 0.80, we can show the effect size for this interaction with 17 Ss/group, or 68 total, or 34 per site in the behavioral portion and in the imaging portion. To be conservative, we will study up to 100 subjects.

17.3 Describe any procedures that will be used for quality control of collected data.

Response:

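### Neither the stated randomisation nor the section 17.1 model accounts for site or scanner, which costs some precision and matters mainly in the fMRI arm

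*Combined protocol and SAP*

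**What the plan says.** **Randomisation.** The behavioral-arm text of section 10.1 names two stratification factors: "Participants will be randomized by stratifying for education level and sex". The fMRI-arm text of the same section says "Eligible participants will be randomly assigned to one of two groups, EFT or ERT" and names none. Neither says whether allocation is done separately at each site.

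**Sites and scanners.** Section 12.1 places the research at the University at Buffalo and at Virginia Tech. Under section 29.1 each principal investigator recruits at his own site. Section 10.3 (Neuroimaging) states "MRI scanning performed at the Dent Neurologic Institute will be performed on a Philips Ingenia 3T system", and that Virginia Tech scanning "will be performed on a Siemens 3T Tim Trio system outfitted with a 45 mT/m gradient system". The anatomical T1 sequences differ by site. The functional EPI sequence is described as matched across the two sites.

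**Analysis.** Section 17.1 plans a factorial ANCOVA on the randomised factors for delay discounting, executive function and brain activation. Its only covariate rule is "Covariates will be used if significant differences between groups are observed in subject characteristics". No site or scanner term is mentioned, and no harmonisation of scanner data in the analysis is described.

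**Sample size.** Section 17.2 gives 17 per group, 68 in total and 34 per site, for the behavioral and the imaging portions alike, with a planned maximum of 100.

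**The concern.** In a two-site study, an outcome difference between sites that is not modelled goes into the error term. In the fMRI arm there is a concrete source for it: two vendors' hardware behind one activation measure. In the behavioral arm the only sources are differences in local population and staff, so the case there is weaker.

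The covariate rule does not close the gap. Scanner is a feature of the measurement, not of the subject, so as worded the rule may never reach it. The rule also works against the stratifiers. Stratifying on education and sex keeps the groups close on both, so a significance test will seldom flag them, and the model then gives up much of the precision that stratification was meant to buy. At stake is the width of the confidence interval for EFT against ERT, in groups of about 34.

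**Working it through.** **Inputs.** From section 17.2: N = 68, 34 per site, SD 0.28, alpha 0.05, power 0.80, effect size 0.35 (read as Cohen's f). Pooling to EFT against ERT gives 34 per group. The site offset D, in within-site SDs, is not in the documents; I assume 0.25 to 1.0.

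**1. The plan's own figure.** For an F test with 1 numerator df, four cells and noncentrality N × f² = 68 × 0.35² = 8.33, the required N is 67, which four equal cells round up to 68. Power at 68 is 0.811. The stated sample size reproduces for an effect size of 0.35, which I take as given.

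**2. Chance imbalance if allocation ignores site.** The SD of the EFT-ERT difference in the share of subjects from one site is

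- N = 68: √(2 × 0.25 / 34) = 0.121, about 12 points
- N = 100: √(2 × 0.25 / 50) = 0.100, 10 points

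The exact (hypergeometric) calculation at N = 68 gives an SD of 0.122. An imbalance of at least 15 points has probability 0.23, and one of at least 20 points has probability 0.09.

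**3. Would the covariate rule catch it?** Take 21 of 34 against 13 of 34 from one site, a gap of 8/34 = 23.5 points. Chi-square = 68 × (21² − 13²)² / 34⁴ = 68 × 272² / 1,336,336 = 3.76, p about 0.052. Even if site counted as a subject characteristic, a gap this large would not trigger adjustment at the 5% level.

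**4. Size of the loss.** With an even site split, leaving site out multiplies residual variance by 1 + D²/4. The typical (1 SD) chance shift in the EFT-ERT difference is 0.121 × D.

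| D | Variance factor | Share of variance due to site | Typical shift (SD) |
|---|---|---|---|
| 0.25 | 1.016 | 1.5% | 0.03 |
| 0.5 | 1.063 | 5.9% | 0.06 |
| 1.0 | 1.25 | 20% | 0.12 |

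The second and fourth columns are one quantity seen two ways. The variance of the shift is D² × 0.121² = D² × 0.0147. The extra variance of the group difference from the inflated residual is (D²/4) × (2/34) = D² × 0.0147. They must not be added together.

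For scale, the AUC means in section 17.2 imply an EFT-ERT difference of (0.585 − 0.45) / 0.28 = 0.48 SD. The section gives no separate effect size for imaging.

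**5. Power at N = 68**, by the share R² of outcome variance due to site. If 0.28 is the within-site SD, omitting site turns f into 0.35 × √(1 − R²). If 0.28 is the total SD, including site turns f into 0.35 / √(1 − R²), with one df spent.

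| R² | 0.28 within-site: site omitted | site included | 0.28 total: site omitted | site included |
|---|---|---|---|---|
| 0 | 0.811 | 0.811 | 0.811 | 0.811 |
| 5% | 0.791 | 0.811 | 0.811 | 0.830 |
| 10% | 0.769 | 0.811 | 0.811 | 0.850 |
| 20% | 0.720 | 0.811 | 0.811 | 0.888 |

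A site term that explains nothing leaves power at 0.811.

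**The case against.** Several points on the other side stand.

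- **Matched functional sequence.** Section 10.3 matches the EPI sequence across sites and gives one set of functional parameters. The sequence settings that differ by site are for the anatomical scans. Sections 14.4 and 29.1 add common training and quality control on a common protocol. All of this narrows a site offset, but the hardware still differs. Section 10.3 also refers to a section 6.6.3 that is not in this document, so any further cross-site handling described there cannot be checked.
- **Silence is not proof.** A reader might infer that allocation ignores site. The documents do not say so; they leave it unspecified. The 34 per site in section 17.2 is a recruitment split and settles nothing either way.
- **Not a bias.** A reader might infer that the treatment comparison is confounded by site. With random allocation the expected imbalance is zero, and the unadjusted standard error already carries the chance imbalance (step 4). Type I error is not raised.
- **Not a scanner problem in both arms.** The stratification sentence belongs to the behavioral arm, where nobody is scanned. The scanner argument applies only to the fMRI arm.
- **Large shifts are a tail case.** Pairing an imbalance of about 24 points with an offset of 0.5 to 1.0 SD gives a shift of 0.12 to 0.24 SD. That joins a roughly 2-SD imbalance (probability about 0.09 for 21 against 13 or worse) to an offset no document supports. The typical shift over the same offsets is 0.06 to 0.12 SD.

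The loss may therefore be small. That does not defend a rule that lets site in only after a significance test, if at all.

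**Conclusion.** The point holds as a cheap gain in precision, stronger in the fMRI arm than in the behavioral arm. Randomisation within site is not specified, site and scanner are absent from the model, and the covariate rule is unlikely to bring them or the stratifiers in.

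The size depends on a site effect the documents do not give. For an offset of 0.25 to 1.0 within-site SD, residual variance is about 2% to 25% higher than it need be. If site explains 5% of variance or less, the loss is small: power goes from 0.811 to 0.791 if SD 0.28 is within-site, and no planned power is lost if it is the total SD. At 10% to 20% it becomes material on the within-site reading (0.769 to 0.720). These figures assume equal site and group sizes and take the plan's effect size of 0.35 as stated. A site term would not repair any separate problem with that effect size.

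**What to change.** 1. In section 17.1, replace the significance-triggered covariate rule with pre-specified terms for site (scanner in the fMRI arm), education and sex in every model, whatever the baseline comparisons show. If enrolment has begun, this can still be settled before the data are analysed.
2. In section 10.1, randomise within site in both arms, using small blocks or minimisation, and state the stratification factors for the fMRI arm. If allocation is already done within site, say so.

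**Cost.** At least three model degrees of freedom: one for site, one for sex and at least one for education. The number of strata doubles. With two sexes and at least two education levels, adding site gives at least eight strata, or about 68 / 8 = 8.5 people each at N = 68, to be spread over four cells in the behavioral arm. That is why small blocks or minimisation are needed.

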2.0 Scientific Endpoints

2.1 Describe the scientific endpoint(s), the main result or occurrence under study.

*NOTE: Scientific endpoints are outcomes defined before the study begins to determine whether the objectives of the study have been met and to draw conclusions from the data. Include primary and secondary endpoints. Some example endpoints are: reduction of symptoms, improvement in quality of life, or survival. Your response should **not** be a date.*

Response: The primary endpoint is the reduction of discounting of the future and increase activation in regions associated with delay of gratification and prospection.

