10.0 Procedures Involved

10.1 *Provide a description of **all research procedures or activities** being performed and when they are performed once a subject is screened and determined to be eligible. Provide as much detail as possible.*

NOTE: This should serve as a blueprint for your study and include enough detail so that another investigator could pick up your protocol and replicate the research. For studies that have multiple or complex visits or procedures, consider the addition of a schedule of events table in in your response.

Response:

Behavioral Arm: Upon arrival to the Division of Behavioral Medicine (G56 Farber Hall), participants will be greeted and escorted to a private interview room where they will be given a verbal explanation about the study and provide documented consent. Two copies of the consent form will be signed by all parties involved, person obtaining consent and the participant. One copy will be obtained by study personnel and one copy will be given to participants for their records. After signing the consent forms, participants will have their blood glucose measured. Participants will then consume a PowerBar and begin completing study related tasks in which they will have their HbA1c, blood pressure, height and weight measured to calculate BMI, and complete measures of delay discounting and study questionnaires including demographics, consumption, alcohol, tobacco substance use, time perspective, and prospective memory. Measures and questionnaires may be completed on either the computer or paper/pencil labelled only with the participant's ID number. About 30-45 minutes after consuming the PowerBar participants will have their blood glucose measured again. In addition, participants will sign forms for release of their relevant medical records to confirm their eligibility (e.g., diagnosis with prediabetes, hypertension and/or hyperlipidemia, MRI

eligibility). Participants will be given a choice as to whether they would like their screening results shared with them and/or with their physician. If participants have values at a certain critical level (e.g. critically high blood pressure) they may be automatically notified. Participants may also complete a urine drug screen to confirm non-substance abuse and female participants may complete a urine pregnancy test to ensure eligibility.

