Subjective Hunger: Participants will be asked to provide subjective ratings of their hunger. Hunger will be assessed using a 5-point Likert scale (anchored by 1-Extremely Full and 5-Extremely Hungry).

Subjective Preferences: Participants may be asked to provide subjective ratings of their food/activity preferences by ranking, rating their liking using a 5-point Likert scale (anchored by 1-Do not like and 5-Like very much), and making choices between their food/activity.

Same Day Food Recall: Participants will be asked if they are willing to eat the study food during a 24-hour recall questionnaire assessing past food behavior

(e.g. what time they ate their last meal, food items consumed in the past 24 hours, etc.). Those who say they are not willing to eat the study food will not be included in the study.

Cue Attention: A Likert-style scale assessing attentiveness to the episodic cues and vividness cues during tasks will be assessed on a scale from 1 to 5, where 1 indicates “not at all” and 5 indicates “very much”.

Delay Discounting: An operational definition of impulsivity is delay discounting, the degree to which a person will discount the value of a larger delayed reward in favor of a smaller immediate reward. Computerized/ experimenter administered assessments will provide participants with choices between a smaller amount of a hypothetical commodity available immediately or a larger amount available later. Participants will make choices between rewards such as money, food, physical activity, and health gains. Two methods will be used to measure discounting, Adjusting Amount and Adjusting Delay.

Adjusting Amount Discounting. The magnitude of the immediate commodity is adjusted until it is subjectively equivalent to the later larger amount. Subjective equivalence will be obtained at delays such as; 1 day, 1 week, 1 month, 3 months, 6 months, and 1 year. To ensure comparison between money and non-monetary rewards, prior to running the discounting programs for food, physical activity and health, participants will indicate the amount of the commodity whose receipt “right now” would be equally valuable to the participants as receiving a set amount of money, for example \$100.

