Adjusting Delay Discounting. The adjusting delay discounting task is a five trial task in which participants are asked how much money they would prefer (e.g. \$500) immediately or a larger reward after a delay (e.g. \$1000). This task is presented on a computer screen and is designed to measure the amount of monetary discounting that occurs when rewards are presented at a delay. This task adjusts the delay to the larger reward and allows for the calculation of k-values. This task will be completed matching each of the traditional tasks parameters (i.e. type and magnitude of the reinforcer).

Executive Function: Cognitive processes, such as planning, cognitive flexibility, working memory, prospective memory, retrospective memory and attention may be measured by using computerized tasks (e.g., with Inquisit) or paper and pencil that involves solving problems, remembering a set of letters or spatial locations while alternating with a distracter tasks, responding to specific stimulus in the presence of an orienting cue, or playing the computer game “The Virtual Week” where users will plan out typical events that could actually happen during the week (e.g., taking their medication, calling their friend, picking up their dry cleaning) (Rendell, & Craik, 2000)

Relative Reinforcing Efficacy Food Purchasing Task: The food purchasing task is modified off of the cigarette purchasing task (CPT) that has been used by Jacobs and Bickel (1999) and assesses a number of different metrics of relative reinforcing efficacy. The procedure we will use is a modified version of this procedure and will assess the relative reinforcing efficacy of a range of foods via

an online survey or computerized task. The chosen food will be displayed during the task so that participants have a frame of reference when completing the questionnaire.

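### Delay discounting, a primary endpoint, may be given by computer or by an experimenter, with no rule for which and no masking or separation of the tester

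*Combined protocol and SAP*

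**What the plan says.** Section 2.1 sets the endpoint: "The primary endpoint is the reduction of discounting of the future and increase activation in regions associated with delay of gratification and prospection". It names no task, commodity or metric as primary.

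Section 10.3 (Delay Discounting) gives the mode of measurement: "Computerized/ experimenter administered assessments will provide participants with choices between a smaller amount of a hypothetical commodity available immediately", with a larger amount later as the alternative. It then names two methods, Adjusting Amount and Adjusting Delay. It does not say which mode applies to which participant, session or site.

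Section 10.1 (Behavioral Arm) describes the episodic task that separates EFT from ERT: "The episodic component of the thinking task will occur while the participants are asked to describe what they are imagining about each event". It adds that participants may be told to think about their cues during executive function and discounting tasks. No section says who runs the episodic task, who gives the discounting task, or whether either person knows the assignment. Masking of staff, participants or analysts is not mentioned.

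**The concern.** The outcome is a set of stated preferences between hypothetical rewards, so it depends on how the choices are put. If a person puts them, and that person knows whether the participant has just worked on future or recent events, tone, pacing or prompting could move answers in the expected direction. Such a shift looks the same in the data as an EFT effect, and no later analysis can remove it.

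What is at stake is any comparison of EFT with ERT: the EFT main effect, the EFT-ERT difference within the poverty condition, and the prediction in 1.2 and 17.1 that EFT brings discounting under poverty to the level of ERT subjects in the neutral condition. In 17.1 that comparison group is called wealth.

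**Working it through.** **1. What the text fixes about mode, task by task**

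- Adjusting Delay (10.3): "This task is presented on a computer screen and is designed to measure the amount of monetary discounting". Computer delivery is explicit. This task yields k-values.
- Adjusting Amount (10.3): mode not stated outright. The phrase "prior to running the discounting programs for food, physical activity and health" suggests software, but it lists food, activity and health, not money.
- Choices in the scanner (10.1, fMRI Arm): "the participant will be given a small box with buttons to press in response to the display that appears on the screen". No examiner delivers these, so the point concerns mainly the behavioral arm.
- Measures in general (10.1, first visit): "Measures and questionnaires may be completed on either the computer or paper/pencil". This adds a third mode, though paper is not examiner delivery.

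The power calculation in 17.2 uses AUC. That fits a task giving equivalence points at several delays, which is Adjusting Amount. This is an inference, since 2.1 names no metric. On that reading, the measure behind the sample size is the one whose mode is left open.

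**2. The plan's own figure**

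Inputs from 17.2: effect size 0.35, SD 0.28, alpha 0.05, power 0.80, 17 per group, 68 in total. Treating 0.35 as Cohen's f with 1 numerator df, the noncentrality is f² × N = 0.1225 × 68 = 8.33. Power is then 0.811 and the minimum N is 67, which rounds up to 17 per cell, so 68 reproduces. Whether 0.35 suits the interaction is a separate question, and nothing here depends on it.

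**3. Which contrasts a shift would reach**

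Planned mean AUC (17.2; higher means less discounting):

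| | Neutral | Poverty |
|---|---|---|
| ERT | 0.54 | 0.36 |
| EFT | 0.63 | 0.54 |

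Add the same examiner shift b to both EFT cells.

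- Interaction: (0.54 − 0.36) − [(0.63 + b) − (0.54 + b)] = 0.18 − 0.09 = 0.09. The shift b cancels.
- Poverty main effect, with equal cells: (0.54 + 0.63 + b)/2 − (0.36 + 0.54 + b)/2 = 0.585 − 0.45 = 0.135. The shift b cancels.
- EFT main effect: (0.63 + 0.54 + 2b)/2 − (0.54 + 0.36)/2 = 0.135 + b. Biased by b.
- EFT/poverty against ERT/neutral: (0.54 + b) − 0.54 = b. Biased by b. If EFT did nothing, EFT/poverty would sit at 0.36, which is 0.18 below ERT/neutral. Shifts of 0.02, 0.05 and 0.09 would shrink that gap to 0.16, 0.13 and 0.09.

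**4. Illustration for an EFT main-effect test**

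Assume no true EFT effect, a two-sided 5% test (17.2 does not state sidedness), and a shift b affecting all participants.

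SE = SD × √(4/N). At N = 68 this is 0.28 × √(4/68) = 0.068. At N = 100, the upper figure in 17.2, it is 0.28 × √(4/100) = 0.056.

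Error rate = Φ(b/SE − 1.96) + Φ(−b/SE − 1.96).

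| Assumed shift b (AUC) | Share of planned 0.135 | N = 68 | N = 100 |
|---|---|---|---|
| 0 | 0% | 5.0% | 5.0% |
| 0.02 | 15% | 6.0% | 6.5% |
| 0.05 | 37% | 11.4% | 14.5% |
| 0.09 | 67% | 26.3% | 36.2% |

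The value 0.09 equals the plan's EFT-ERT difference in the neutral condition (0.63 − 0.54). The documents give no estimate of b. If only half the participants were tested by an experimenter, the average shift would halve: 0.05 becomes 0.025, and the error at N = 68 falls between 6.0% and 11.4%.

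**The case against.** The strongest reply is that the exposure may be small. One of the two methods is on screen, the other is described as a program, and scanner choices use a button box. The slash in 10.3 could mean a computer task that a staff member merely starts. The questionnaire attachment cited in 10.3, which is not among the documents, may fix the mode. Section 16.1 already has the experimenter watching sessions by closed-circuit television, and 14.4 and 29.1 cite manuals and common training. All of this stands and limits the likely size. It does not close the gap: the wording still permits examiner delivery, and neither the manuals nor the training is said to cover masking or assessor separation.

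A second reply is that the tests named in 17.1 are the poverty main effect and the interaction, and a uniform shift reaches neither. That is correct. The prediction about the EFT/poverty level remains exposed.

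A reader might infer more than the documents support:

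- That the tester has just run the same participant's episodic interview. Section 14.2 has research assistants running participants and 21.2 puts an interviewer in the room during interviews, so this is plausible, but no section says it.
- That the trial is declared open-label. It is not; masking is simply not mentioned.
- That mixed modes bias the result. Nothing suggests that mode would differ by group. Variation unrelated to group adds noise, and 17.1 plans between-group comparisons with no mention of a change score between sessions.

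**Conclusion.** The point holds as an inexpensive improvement to the design. The plan permits experimenter delivery of a primary endpoint, gives no rule for when it is used, and neither masks the tester nor separates the tester from the episodic task. Bias in EFT-versus-ERT comparisons is therefore possible. Its size cannot be derived from the documents.

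The illustrative error rates of about 6%, 11% and 26% at N = 68 rest on assumed shifts, on experimenter testing of every participant, and on an EFT main-effect test. They should not be read as inflation of the poverty main effect or the interaction, which a uniform shift leaves unbiased. Nor would computer delivery make the comparison free of expectation effects: participants know their own cues and may be told to use them while choosing.

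**What to change.** In 10.3, remove experimenter administration as an option for delay discounting. Require the self-administered computer version, with identical on-screen instructions, for all groups, sessions and sites. State that the experimenter observes through the closed-circuit monitor already described in 16.1.

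The cost is mainly protocol wording. Computer tasks and room monitoring already exist, and 6.2 already excludes people with medical conditions that would affect prolonged computer use. The downside is that some participants may need a short practice block, which should be standard for all groups.
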